## Appendix 6. Hepatic Monitoring Tests for Treatment-Emergent Abnormality

---

Selected tests may be obtained in the event of a treatment emergent hepatic abnormality and may be required in follow up with patients in consultation with the Lilly CRP/CRS.

### Hepatic Monitoring Tests

Hepatic Hematologya	Haptoglobina
Hemoglobin (HGB)	
Hematocrit (HCT)	
Erythrocytes (RBC)	
Leukocytes (WBC)	
Neutrophils b	
Lymphocytes	Hepatic Coagulationa
Monocytes	Prothrombin Time (PT)
Eosinophils	Prothrombin Time, INR
Basophils	
Platelets (PLT)	
Hepatic Chemistrya	Hepatic Serologiesa,c
Total bilirubin	Hepatitis A antibody, total
Direct bilirubin	Hepatitis A antibody, IgM
Alkaline phosphatase	Hepatitis B surface antigen
Alanine aminotransferase (ALT)	Hepatitis B surface antibody
Aspartate aminotransferase (AST)	Hepatitis B Core antibody
Gamma-glutamyl transferase (GGT)	Hepatitis C antibody
Creatine phosphokinase (CPK)	Hepatitis E antibody, IgG
	Hepatitis E antibody, IgM
	Recommended Autoimmune Serology:
	Anti-nuclear antibody a
	Anti-smooth muscle antibody a
	Anti actin antibody a

Abbreviations: Ig = immunoglobulin; INR = International Normalised Ratio; RBC = red blood cells; WBC = white blood cells.

a Assayed by Lilly-designated laboratory.

b Neutrophils reported by automated differential hematology instruments include both segmented and band forms. Whenever a manual differential is needed to report the neutrophils, the segmented and band forms should be added together and recorded on the CRF, unless the CRF specifically provides an entry field for bands.

c Reflex/confirmation dependent on regulatory requirements and/or testing availability.

---

## Appendix 7. Creatinine Clearance Formula

---

**Note:** This formula is to be used for calculating creatinine clearance (CrCl) from **local laboratory results only**.

*For serum creatinine concentration in mg/dL:*

$$\text{CrCl} = \frac{(140 - \text{age}^a) \times (\text{wt}) \times 0.85 \text{ (if female), or } \times 1.0 \text{ (if male)}}{72 \times \text{serum creatinine (mg/dL)}}$$

*For serum creatinine concentration in  $\mu\text{mol/L}$ :*

$$\text{CrCl} = \frac{(140 - \text{age}^a) \times (\text{wt}) \times 0.85 \text{ (if female), or } \times 1.0 \text{ (if male)}}{0.81 \times \text{serum creatinine ( $\mu\text{mo/L}$ )}}$$

---

a age in years, weight (wt) in kilograms.

Reference: Cockcroft and Gault 1976.

## Appendix 8. Dose-Finding Algorithm of the Modified Toxicity Probability Interval (mTPI-2) Method Showing Number of Patients Treated

		Number of Patients																			
		1	2	3	4	5	6	7	8	9	10	11	12	13	14	15	16	17	18	19	20
Number of DLTs	0	E	E	E	E	E	E	E	E	E	E	E	E	E	E	E	E	E	E	E	
	1	D	D	S	S	E	E	E	E	E	E	E	E	E	E	E	E	E	E	E	
	2		DU	D	D	D	S	S	S	E	E	E	E	E	E	E	E	E	E	E	
	3			DU	DU	D	D	D	S	S	S	S	E	E	E	E	E	E	E	E	
	4				DU	DU	DU	D	D	D	D	D	S	S	S	S	S	E	E	E	
	5					DU	DU	DU	DU	DU	D	D	D	D	S	S	S	S	S	S	
	6						DU	DU	DU	DU	DU	DU	D	D	D	D	D	S	S	S	
	7							DU	DU	DU	DU	DU	DU	D	D	D	D	D	D	D	
	8								DU	D	D	D	D								
	9									DU											
	10										DU										
	11											DU									
	12											DU									
	13												DU								
	14												DU								
	15													DU							
	16														DU	DU	DU	DU	DU	DU	
	17															DU	DU	DU	DU	DU	
	18																DU	DU	DU	DU	
	19																	DU	DU	DU	
	20																		DU	DU	

E: Escalate to the next higher dose; S: Stay at the same dose; D: De-escalate to the previous lower dose; DU: De-escalate to the previous lower dose and the current dose will never be used again in the trial;

Source: Guo et al. 2016.

The number of patients dosed at a given dose level is shown in the columns (X-axis), while the number of DLTs experienced is shown in the rows (Y-axis). The rules in this figure will be used for each dose level evaluated; the patient numbers and DLTs do not carry over from cohort to cohort. By locating the intersection of the number of patients dosed and the number of DLTs, 1 of 4 predefined rules is used:

- E: Escalate the dose
- S: Stay at the same dose
- D: De-escalate the dose
- DU: De-escalate the dose due to unacceptable toxicity. The dose cannot be re-escalated to this dose level at a future point in the escalation.

For example, within a cohort:

- If 1 of 3 patients experiences a DLT, stay at the same dose (see “S” in column 3, row 1). The fourth patient must be treated at the same dose level.
- If 1 of 6 patients experiences a DLT, escalate the dose (see “E” at column 6, row 1).
- If 2 of 3 patients experience a DLT the dose to treat the next patient is de-escalated (see “D” at column 3, row 2).
- If 5 of 7 patients experience a DLT, the dose is determined to be unacceptably toxic, and the previous dose is defined as the MTD.

---

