#### 7.2.2.1. Dose Escalation Method

An mTPI-2 method will be used to identify an RP2D for LY3434172, taking into consideration available PK and pharmacodynamic data from previous dose levels. Each cohort in this study will enroll at least three patients.

Like the 3+3 design, the mTPI-2 method incorporates prespecified escalation rules. In contrast, the mTPI-2 method is based on quantitative models that incorporate uncertainty into the decision rules, thereby allowing more precise RP2D selection. If three or six patients are enrolled in a cohort, the escalation rule parallels a traditional 3+3 design. However, it allows flexible number of patients in a cohort. For example, with two DLTs per six patients enrolled, the mTPI-2 would recommend staying at the current dose, as analogy to one DLT per three patients enrolled in 3+3 design; therefore, it allows more patients for a more precise estimate of the DLT rate at this dose level.

[Appendix 8](#) provides the mTPI-2 escalation rules for any cohort size up to 20 patients.

Following a discussion between the Lilly CRP/CRS and the investigators, a more conservative dose selection may be applied to the next cohort (for instance, if PK/pharmacodynamic data suggest that further dose increase would not be expected to yield additional benefit). For example, if the rule indicates “E” to escalate, the dose may stay at the current dose level, be de-escalated to a lower level, or escalation may cease. In the mTPI-2, the cohort size is not fixed. However, each cohort in this study will contain a minimum of three patients, unless the escalation rules dictate that the dose should be de-escalated (“D” or “DU”). Doses can be escalated, de-escalated, and re-escalated following the rules in [Appendix 8](#). If the dose decision was “DU,” the dose cannot be re-escalated to that level. This study is designed to identify a dose level with a dose-limiting target toxicity rate of 30%. The mTPI-2 method considers an equivalence interval (EI) around the target toxicity rate. For this study, the EI is elicited to be (25%, 35%), resulting in the rules in [Appendix 8](#).

Intermediate and/or higher dose as well as alternative schedules of administration will be explored if deemed necessary after discussion between Lilly and investigators and taking into account patient safety and PK/pharmacodynamics data. If necessary, additional patients may be enrolled to further assess PK/pharmacodynamics or tolerability.

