### 7.6.1. *Evaluable Patients*

#### 7.6.1.1 DLT-Evaluable Patients in Phase 1 Dose Escalation

Dose escalation refers to Cohort A1 to A5 or Cohort A1 to A6 (if Cohort A6 is opened).

A patient will be DLT evaluable if he or she experiences a DLT during the DLT observation period and has received at least one dose of study drug.

If a patient does not experience a DLT during the DLT observation period, he or she will be DLT evaluable if he or she receives all assigned doses of study drug(s) during the DLT observation period

Patients who receive all doses of study drug but discontinue from study treatment before the end of the DLT observation period will be considered DLT evaluable for the assessment of a dose level, provided it can be documented that the patient did or did not experience a DLT within the DLT observation period.

Patients who are not DLT evaluable may be replaced to ensure that enough patients complete the DLT observation period at each dose level, unless accrual to that cohort has stopped due to a DLT.

A patient may be deemed non-evaluable for assessment of a dose level in the event the patient experiences an AE which would meet DLT criteria, and furthermore has been determined through discussion between investigator and Lilly CRP/CRS to most likely be related to a concomitant medication or a prior line of immune therapy (in the case of irAEs) due to previously established linkage.

To ensure collection of adequate PK or biomarker data, patients who complete the DLT observation period but who do not have a valid PK or biomarker assay result may be replaced, upon consultation with the investigator(s) and the Lilly CRP/CRS, unless accrual to that cohort has stopped because of a DLT. Patients who are replaced for purposes of the PK or biomarker analysis are still considered DLT evaluable.

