#### 6.2.1. Populations

The following population will be defined for this study:

**Entered population:** will include all patients who sign the informed consent document.

**Enrolled/safety population:** will include all patients who received any quantity of study treatment (LY3434172), regardless of their eligibility for the study. The safety and efficacy evaluation will be performed based on the first dose of study treatment a patient actually received. This population will be used for all dosing/exposure, safety, and efficacy analyses.

**Dose-limiting toxicity–evaluable population:** will include all patients from the study who have completed the DLT observation period (Cycle 1) or discontinued treatment before the end of the DLT observation period but with a documented DLT assessment. Exposure and safety summaries may be repeated for this population.

**Pharmacokinetic population:** will include all enrolled patients from whom a valid assay result (according to laboratory guidelines) has been obtained.

**Biomarker population:** will include the subset of enrolled patients from whom a valid assay result has been obtained. No imputation will be performed for missing data due to the limitation of small sample size.

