### **6.12.2. Dose-Limiting Toxicities and DLT-Equivalent Toxicities**

Definitions of DLTs and DLT-equivalent toxicities (DETs) are provided in Section 7.2.2.2 of Protocol JZEA.

Dose-limiting toxicities will be summarized and listed for the DLT-evaluable population (defined in Section 7.6.1 of Protocol JZEA), and DETs will be listed and summarized for the safety population.

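### The mTPI-2 grid is indexed by patients dosed, not DLT-evaluable patients, so a literal count of a non-evaluable patient can move a decision one step toward a higher dose

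*Protocol*

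**What the plan says.** **The grid.** Protocol Appendix 8 states: "The number of patients dosed at a given dose level is shown in the columns (X-axis". Its lookup instruction repeats the term: "By locating the intersection of the number of patients dosed and the number of DLTs". The title says *Treated*. Evaluability is not mentioned. The method text in 7.2.2.1 describes the same rule in terms of patients *enrolled*.

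**Evaluability.** Under protocol 7.6.1.1, a patient who has a DLT is evaluable after at least one dose. For a patient without a DLT, "he or she will be DLT evaluable if he or she receives all assigned doses of study drug(s) during the DLT observation period". Non-evaluable patients may be replaced. A patient whose event meets DLT criteria may be ruled non-evaluable if it is attributed to a concomitant medication or to earlier immune therapy. The note under Table JZEA.8 also allows a confounded case to be treated as not evaluable for dose selection.

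**The SAP.** Section 6.2.1 defines the DLT-evaluable population as patients who "completed the DLT observation period (Cycle 1) or discontinued treatment before the end of the DLT observation period but with a documented DLT assessment". It sets no dosing condition. Section 6.12.2 then says: "Dose-limiting toxicities will be summarized and listed for the DLT-evaluable population (defined in Section 7.6.1 of Protocol JZEA".

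**The concern.** The escalation rule and the evaluability rule use different counts, and no sentence connects them. Two kinds of patient fall in the gap:

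- a DLT-free patient who missed an assigned dose in the window;
- a patient whose event was ruled not evaluable.

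Under 7.6.1.1 neither should inform the dose level. Under the literal wording of Appendix 8 both add one to the column and nothing to the row. That lowers the apparent DLT rate and can only leave the grid decision unchanged or make it more permissive. In a first-in-human study whose primary endpoint is DLTs, the input to the dose rule should not depend on which section the team has open.

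**Working it through.** **Inputs.** Target DLT rate 30% and equivalence interval 25% to 35% (protocol 7.2.2.1). Grid cells and worked examples from Appendix 8.

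**Step 1: reproduce the grid.** I rebuilt mTPI-2 with subintervals 0.10 wide around the equivalence interval, taking the decision from the subinterval with the largest unit probability mass. DU applies when P(p > 0.30 | data) > 0.95. The Beta(1,1) prior and the 0.95 cut-off are my assumptions; the documents give neither. The rebuild returns all four worked examples (1/3 = S, 1/6 = E, 2/3 = D, 5/7 = DU) and the 2/6 = S example in 7.2.2.1. Rows 0 to 2 match cell for cell. In the text copy I used, rows 0 to 7 have each lost one cell; allowing for that, rows 3 to 7 agree too.

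**Step 2: find the cells that one extra DLT-free patient changes.**

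| DLTs | Evaluable count | Literal count | Change |
|---|---|---|---|
| 1 | 4 = S | 5 = E | stay to escalate |
| 2 | 8 = S | 9 = E | stay to escalate |
| 2 | 5 = D | 6 = S | de-escalate to stay |
| 3 | 8 = D | 9 = S | de-escalate to stay |

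The first three lines can be read directly from the table. The fourth rests on the rebuild, because row 3 is one cell short in my copy; counting cells there would put the change at 7 to 8. It should be checked against the original page.

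**Step 3: find where nothing changes.** Three evaluable patients plus one: 0/3 and 0/4 = E; 1/3 and 1/4 = S; 2/3 and 2/4 = D; 3/3 and 3/4 = DU. Six plus one: the only change is 4/6 = DU to 4/7 = D.

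**Step 4: size at four evaluable patients.** With true rate p:

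- Four evaluable patients escalate only with 0 DLTs: (1 − p)^4. At 30%: 0.7^4 = 0.240.
- Counting one extra patient with no DLT risk, they escalate with at most 1 DLT: (1 − p)^4 + 4p(1 − p)^3. At 30%: 0.240 + 0.412 = 0.652.
- If the extra patient carries half the risk, the second term is multiplied by (1 − p/2). At 30%: 0.240 + 0.412 × 0.85 = 0.590.
- Five evaluable patients: (1 − p)^5 + 5p(1 − p)^4. At 30%: 0.168 + 0.360 = 0.528.

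| True DLT rate | 4 evaluable | 4 + 1, no risk | 4 + 1, half risk | 5 evaluable |
|---|---|---|---|---|
| 30% | 24.0% | 65.2% | 59.0% | 52.8% |
| 35% | 17.9% | 56.3% | 49.6% | 42.8% |
| 40% | 13.0% | 47.5% | 40.6% | 33.7% |
| 50% | 6.3% | 31.3% | 25.0% | 18.8% |

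Part of the rise from 24.0% to 65.2% comes simply from moving to the five-patient column. Against five evaluable patients, the excess at 30% is 65.2 − 52.8 = 12.4 percentage points with no risk and 59.0 − 52.8 = 6.2 with half risk.

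At eight evaluable patients, 30% true rate: 25.5%, rising to 55.2% with one extra no-risk patient; nine evaluable patients give 46.3%.

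**Step 5: compare the SAP with the protocol.** Two differences appear. SAP 6.2.1 has no all-assigned-doses condition. It also limits the window to Cycle 1, whereas protocol 7.2.2.2 uses Cycles 1 and 2 (42 days) for Cohorts A7 and A8. SAP 6.12.2 sends the reader to protocol 7.6.1, so the SAP holds two definitions of one population.

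**The case against.** The strongest reply is that the protocol, read as a whole, means evaluable patients. Section 7.6.1.1 is headed as applying to dose escalation and speaks of evaluability for assessing a dose level. The note under Table JZEA.8 refers to dose selection. Counting excluded patients would defeat both. Escalation also needs sponsor and investigator agreement, recorded in writing (7.2.2), and 7.2.2.1 permits a more cautious choice when the grid says escalate. This largely stands as evidence of intent, and it makes the error avoidable. It does not supply the denominator: the caution is optional, and the only text that tells the team how to read the grid says *dosed*.

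Three stronger readings are tempting, but the documents do not support them.

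- *The SAP definition drives escalation.* It does not. The SAP uses its DLT-evaluable set for the DLT summary and for optional exposure and safety summaries. Appendix 8 alone produces the change of decision.
- *Under-dosed patients are bound to occur, because Table JZEA.10 withholds treatment for several Grade 2 events.* Section 7.4 allows no dose modification in Cycle 1, yet also requires withholding for drug-related toxicity. Those statements must be reconciled. Missed doses in the window are possible, and the replacement provision anticipates non-evaluable patients, but their frequency cannot be derived.
- *The probabilities in the working are the risk of a wrong escalation.* They are conditional on such a patient being present and being counted. The documents give no probability for either.

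**Conclusion.** The point holds as an internal inconsistency: wrong as written, moderate severity. Appendix 8 states a count that conflicts with the protocol's own evaluability rule, and following it literally can relax a decision by one step.

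The effect is confined to particular cells. Up to nine evaluable patients, stay becomes escalate only at 1/4 to 1/5 and 2/8 to 2/9. At a minimum cohort of three evaluable patients, one extra patient has no effect. Where it does apply it is not small: at four evaluable patients and a 30% true rate, the chance of an escalate reading goes from 24% to between 59% and 65%, depending on whether the extra patient carries half the DLT risk or none.

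These figures assume independent patients with a common DLT rate and a team that reads *dosed* literally. The SAP discrepancy affects only the reported DLT denominator.

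**What to change.** 1. In Appendix 8 (title, column definition and lookup instruction) and in 7.2.2.1, state that the grid count is the number of DLT-evaluable patients as defined in Section 7.6.1.1.
2. In SAP 6.2.1, replace the DLT-evaluable definition with that of protocol 7.6.1.1, including the all-assigned-doses condition for patients without a DLT, and use the cohort-specific windows in protocol 7.2.2.2. This also removes the conflict with SAP 6.12.2.
3. At each dose decision, list dosed but non-evaluable patients with the reason.
4. Reconcile the two statements in 7.4 about withholding during Cycle 1, since they bear on who becomes non-evaluable.

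The cost of items 1 to 3 is a few words in the protocol, one SAP paragraph and a short listing. Some decisions will wait for a replacement patient, which 7.6.1.1 already allows.

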## Appendix 9. Definition of Woman of Childbearing Potential

---

Definitions:

**Woman of Childbearing Potential (WOCBP)**

A female is not considered to be of childbearing potential due to surgical sterilization confirmed by medical history (at least 6 weeks post-surgical bilateral oophorectomy with or without hysterectomy or tubal ligation) or menopause.

Menopausal women include women with either:

- a. spontaneous amenorrhea for at least 12 months, not induced by a medical condition such as anorexia nervosa, and not taking medications during the amenorrhea that induced the amenorrhea (for example, oral contraceptives, hormones, gonadotropin-releasing hormone, antiestrogens, selective estrogen receptor modulators, or chemotherapy), or
- b. spontaneous amenorrhea for 6 to 12 months and a follicle-stimulating hormone level >40 mIU/mL.

For individuals with permanent infertility due to an alternate medical cause other than the above, (for example, mullerian agenesis, androgen insensitivity), investigator discretion should be applied to determining study entry.

Note: Documentation can come from the site personnel's review of the participant's medical records, medical examination, or medical history interview.

Exceptions to those listed above would be if female and of childbearing potential, has a negative serum or urine pregnancy test within 7 days prior to the first dose of study medication, agrees to use a highly effective method of birth control during the study and for 6 months following the last dose of the study drugs, and is not breastfeeding. If the urine pregnancy test is positive or cannot be confirmed as negative, a serum pregnancy test will be required.

---

## **Appendix 10. Protocol Amendment J1E-MC-JZEA(b) Summary A Phase 1 Study of LY3434172, a Bispecific Antibody Administered as a Monotherapy in Advanced Solid Tumors**

---

### **Overview**

Protocol J1E-MC-JZEA(a), A Phase 1 study of LY3434172, a bispecific antibody administered as a monotherapy in advanced solid tumors, has been amended. The new protocol is indicated by Amendment (b) and will be used to conduct the study in place of any preceding version of the protocol.

The overall changes and rationale for the changes made to this protocol are as follows:

- The following phrase was made applicable for Cohorts A1 to A5/A6: “Once dose-limiting toxicity (DLT) period is completed for respective Cohorts A1 to A5/6 up to approximately 12 to 15 additional patients may be added to two dose levels selected from these cohorts.” Corresponding revisions were made to Synopsis (Overall Design), Section 5.1 (Overall Design), Section 7.1 (Treatment Administered), Section 10.1 (Sample Size Determination), and Section 10.3.4 (Interim Analyses).
- A clarification of the 4-hour observation period and the sampling times relative to infusion time was made throughout the document. All observation periods and post-dose sampling times are now relative to the end of LY3434172 administration/infusion.
- A correction to the timing of tumor imaging for Cohorts A7 and A8 after Cycle 1 Day 1 was made. For Cycle 3 and beyond, Day 8 visits were deleted from the Schedule of Activities for these cohorts, since there are no infusions and sample collections for the D8 visits.
- A correction to vital signs collected during the post study treatment schedule was made to include oxygen saturation.
- A change was made to exclusion criterion 14 in Section 6.2 to clarify active hepatitis and active tuberculosis.
- A statement about repeating screening tests was deleted from Section 6.4.
- A clarification that anaphylaxis will be considered a DLT was made to Section 7.2.2.2.1 and a clarification that study treatment will be immediately and permanently discontinued was added to Table JZEA 9.
- Additional standard safety monitoring language was added to Section 9.4.2.
- Stool sample collections were added to Appendix 4 and clarification of the timing of predose and post dose samples was added to the footnotes.

## Revised Protocol Sections

**Note:** All deletions have been identified by ~~strikethroughs~~.  
All additions have been identified by the use of underscore.

### Section 1. Synopsis

#### Overall Design:

[figure not shown]
Study J1E-MC-JZEA (JZEA) is a multicenter, nonrandomized, open-label Phase 1 study in patients with advanced solid tumors.

Phase 1 study will assess the safety and tolerability of LY3434172, administered as a monotherapy in patients with select advanced solid tumors. Study JZEA will facilitate a thorough safety evaluation and exploration of pharmacokinetics (PK) and pharmacodynamics effects for the every two-week (Q2W) dosing schedule (Cohorts A1 to A6). Once dose-limiting toxicity (DLT) period is completed for respective Cohorts A1 to A5/6 up to approximately 12 to 15 additional patients may be added to two dose levels selected from ~~Cohorts A4, A5/6, these cohorts~~.

...

